8.2.1. Missed Doses of BCV

When a dose of BCV is missed, subjects should take the missed dose as soon as possible, and no later than 2 days prior to the next scheduled dose (i.e., either the next day if the originally scheduled next dose is in 3 days, or within the next 2 days if the originally scheduled next dose is in 4 days).

A subject who normally takes his/her BIW BCV doses on Mondays and Thursdays each week may take a missed Monday dose on Tuesday and a missed Thursday dose on Friday or Saturday.

A subject taking his/her QW BCV doses every Monday should take their missed dose as soon as possible, but may take a missed dose as late as Thursday, which allows 4 days between the late dose and the next scheduled Monday dose.

If the subject cannot take the late dose within these timeframes, it should be omitted and the subject should wait until the next scheduled dosing day to take his/her next dose. The original dosing schedule should be resumed following any missed or omitted doses.

It is important to capture the actual dates and times of all BCV doses and whether each dose was taken with food in the electronic case report form (eCRF), even if the actual dates and times deviate from scheduled. E-dairies will be provided to the subjects to facilitate the collection of this information when outpatient.

8.2.2. Vomiting After Dosing

If a subject vomits within 30 minutes of receiving a dose of BCV, the subject may be re-dosed, as described in the pharmacy manual. If the vomiting occurs more than 30 minutes after dosing, it should be assumed that there was significant absorption of BCV, in which case, the subject should not be re-dosed.

8.3. BCV Dosing Algorithm and Management

In this study, BCV will be dosed using a response-driven approach to the duration of treatment based on both viral response and the emergence of BCV-related toxicity. BCV therapy will be continued until the virus is cleared from the plasma, unless toxicity stopping criteria are met. Investigators will be specifically trained on the management of BCV toxicity.

8.3.1. BCV Dosing Algorithm Based on Virologic Response

The duration of BCV treatment will be determined using results from the designated central virology laboratory only.

In the absence of toxicity requiring dose interruption, BCV will be administered BIW for up to 16 weeks or until plasma AdV viremia is confirmed as undetectable (i.e., two consecutive plasma viral load results of “undetectable” as reported by the designated central virology laboratory). The confirmatory sample must be drawn no sooner than 7 days (6 full calendar days) and no later than 14 days (13 full calendar days) after the last sample was drawn. Once AdV viremia is confirmed as undetectable, BCV will be discontinued. If AdV viremia is subsequently confirmed at ≥ 1000 copies/mL by the designated central virology laboratory, BCV dosing may be re-initiated, unless precluded by the BCV toxicity guidelines (see Section 8.4). See [Appendix 3](#) for a flow chart of the BCV dosing algorithm.

8.3.2. Safety Monitoring, Management, and Criteria for BCV Dose Adjustment

Subjects with signs or symptoms suggestive of BCV-related toxicity must be managed according to the guidelines described in this section. See [Appendix 4](#) for a flow chart for BCV toxicity management.

Investigators should pay particular attention to GI signs and symptoms when questioning subjects about adverse reactions at every study visit. In particular, when a decrease in serum albumin of ≥ 0.4 g/dL (SI: ≥ 4 g/L) to < 3.0 g/dL (SI: < 30 g/L) (suggestive of protein losing enteropathy) is noted, investigators should intensify their questioning of subjects with respect to symptoms of diarrhea (recognizing that albumin loss does not discriminate between GI GVHD and BCV-associated diarrhea) and remind subjects to record daily diarrhea symptoms in the e-diary.

All AEs should be graded in accordance with the protocol-defined scale (CTCAE scale); management of GI-related AEs and hepatobiliary laboratory abnormalities and BCV dosing guidelines are based on CTCAE severity/intensity grading, as described below. The CTCAE severity grading for diarrhea, which is defined as “characterized by frequent and watery bowel movements,” is summarized in [Table 7](#).

Table 7: CTCAE Grading Scale for Diarrhea

Grade	Definition:
Grade 1	Increase of < 4 stools per day over baseline; mild increase in ostomy output compared to baseline
Grade 2	Increase of 4 to 6 stools per day over baseline; moderate increase in ostomy output compared to baseline
Grade 3	Increase of ≥ 7 stools per day over baseline; incontinence; hospitalization indicated; severe increase in ostomy output compared to baseline; limiting self-care ADLs ^a
Grade 4	Life-threatening consequences; urgent intervention indicated
Grade 5	Results in death

^a Self-care ADLs (activities of daily living) refer to bathing, dressing and undressing, feeding self, using the toilet, taking medications, and not bedridden.

Note: Pre-transplant stool output (= baseline).

Educational and risk minimization materials will be used in this study to highlight the potential for BCV-related diarrhea in subjects who are randomized to receive BCV. For example, a reference card summarizing the management of diarrhea may be left in the subject's bedside notes to serve as a reminder to the physicians and nurses caring for the patient to inquire about diarrheal symptoms. Also, the subject or the subject's caregiver may be given a patient alert card describing the potential for BCV-related GI problems and the actions they should take if the subject experiences diarrhea while taking BCV. Examples of the reference and patient alert cards are provided in the SRM.

Please contact the Chimerix Medical Monitor (or designee) for questions related to toxicity management.

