5.3.3. Safety Endpoints

- Incidence of treatment-emergent AEs (TEAEs), particularly those of \geq CTCAE Grade 3 severity and SAEs
- Incidence of treatment-related AEs, particularly those of \geq CTCAE Grade 3 severity and SAEs
- Incidence of AEs resulting in permanent BCV or other anti-AdV drug discontinuation
- Incidence of AEs requiring BCV or other anti-AdV drug interruption
- Incidence of AEs requiring dose modification or consolidation of BCV or other anti-AdV drug
- Incidence of fatal AEs
- Incidence of and time to CTCAE Grade 2 or higher diarrhea
- Incidence of doubling, tripling, or quadrupling of baseline serum creatinine
- Incidence of need for renal replacement therapy
- Incidence of $\geq 1/2/3$ CTCAE grade increases from baseline for safety laboratory parameters of interest (by visit, maximum on-treatment, last on-treatment, last on-study)
- Distributions of change from baseline over time for central safety laboratory parameters of interest (by visit, maximum on-treatment, last on-treatment, last on-study)
- Assessment of all deaths that occur through Week 16 and in follow up through Week 36

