8.7.1. Subject Electronic Diary

All subjects will be provided with software and/or devices equipped with an e-diary for collection of study information. Subjects or caregivers will record daily diarrhea symptoms and may record the dates and times of doses of BCV and whether each dose was taken with food (for

subjects randomized to the BCV treatment arm) in the e-diary through Week 16 (see Section 11.6). While subjects are inpatients, the information may be entered in the e-diary by study staff.

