8.8. Randomization and Blinding

All treatments will be administered under open-label conditions.

Subjects who meet all applicable eligibility criteria will be randomized to one of two treatment arms (BCV or SoC) in a 2:1 ratio using an automated IV/WRS. During randomization, subjects will be stratified based on the following variables:

- last (non-baseline) screening AdV viremia ($\geq 10,000$ copies/mL vs. $< 10,000$ copies/mL)
- time from transplant to randomization (≥ 28 days vs. < 28 days), and
- T cell-depletion methodology (receipt of alemtuzumab or ex vivo depletion vs. receipt of ATG)

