11.9.3. Recording Adverse Events

AEs spontaneously reported by the subject, in response to an open question from study personnel and/or revealed by observation will be recorded during the study. For each AE, the investigator will evaluate and report the onset date, resolution date, intensity (severity), causality (relatedness to BCV or other anti-AdV drug, as applicable), action taken (with BCV or other anti-AdV drug as well as other action taken), seriousness, outcome (if applicable), and whether it caused the subject to discontinue BCV or other anti-AdV drug.

All AEs and SAEs should be recorded on the appropriate AE module of the eCRF. The intensity (severity) of all AEs will be graded according to the NIH/NCI CTCAE grading scales. The CTCAE scales provide unique clinical descriptions of severity for each AE based on the following general guideline:

- Grade 1:** Mild; asymptomatic or mild symptoms; clinical or diagnostic observations only; intervention not indicated
- Grade 2:** Moderate; minimal, local or non-invasive intervention indicated; limiting age-appropriate instrumental ADL (see below)
- Grade 3:** Severe or medically significant but not immediately life-threatening; hospitalization or prolongation of hospitalization indicated; disabling; limiting self-care ADLs
- Grade 4:** Life-threatening consequences; urgent intervention indicated
- Grade 5:** Death related to AE

Instrumental ADLs refer to preparing meals, shopping for groceries or clothes, using the telephone, managing money, etc. Self-care ADLs refer to bathing, dressing and undressing, feeding self, using the toilet, taking medications, and not bedridden.

A copy of the full NIH/NCI CTCAE grading tables is provided in the SRM.

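### The Grade 2 or higher diarrhea endpoint has no named data source; its likely source, investigator-graded AEs in an open-label trial, is open to unequal ascertainment, and no stated analysis uses the stool e-diary kept in both arms

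*Combined protocol and SAP*

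**What the plan says.** Section 5.3.3 lists "Incidence of and time to CTCAE Grade 2 or higher diarrhea" as a safety endpoint. It does not say which records the endpoint is derived from. Section 8.8 states "All treatments will be administered under open-label conditions".

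For adverse events, Section 11.9.3 describes collection as "AEs spontaneously reported by the subject, in response to an open question from study personnel and/or revealed by observation", with the investigator grading by CTCAE. Section 8.3.2 adds materials "to highlight the potential for BCV-related diarrhea in subjects who are randomized to receive BCV". One example is a card in the bedside notes, "to serve as a reminder to the physicians and nurses caring for the patient to inquire about diarrheal symptoms"; another is an alert card for the child or caregiver. Both are worded as optional. The same section says "Investigators should pay particular attention to GI signs and symptoms when questioning subjects about adverse reactions at every study visit". That sentence names no arm, although it sits within the BCV toxicity guidance.

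For the diary, Section 8.7.1 states "All subjects will be provided with software and/or devices equipped with an e-diary for collection of study information". Section 11.6 says that stool number and Bristol consistency are entered daily and that the diary is gone over with the family at each visit. The synopsis lists it among the safety assessments, through Week 16. No endpoint in Section 5.3 and no analysis in Section 12 mentions it.

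**The concern.** Diarrhea is presented as the key BCV toxicity (4.2.3.1). Safety and tolerability are part of the primary objective (5.1), and Section 4.3.1 treats the revised toxicity guidance as something the trial is meant to assess. The between-arm comparison of Grade 2 or higher diarrhea will therefore be read closely even if it is only descriptive.

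If the comparison rests on AEs graded by unblinded investigators, a difference between arms mixes the drug's effect with how hard each arm was asked, how often a grade had to be decided, and what cause was assigned. Daily stool counts collected the same way in both arms could help separate these, but the protocol gives them no analytic role.

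**Working it through.** **Step 1. Trace the source.** Section 12.6 has two subsections, adverse events and laboratory results. CTCAE grading of diarrhea is tied to AEs in 8.3.2 and 11.9.3. AEs are therefore the natural default, but this is an inference: the tables listed in 12.6.1 cut severity only at Grade 3 and contain no time-to-event summary, so as written they do not deliver the endpoint either.

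**Step 2. Set the arms side by side.**

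| Feature | BCV | SoC |
|---|---|---|
| Diarrhea materials and optional cards (8.3.2) | Yes | None described |
| Protocol action triggered at Grade 2 (8.3.2.2) | Yes, in children with Grade 1 or no diarrhea at baseline | None; local practice (8.1) |
| Non-fatal events attributed to AdV (11.9.1) | Need not be AEs | Need not be AEs |
| TEAE window (12.6.1) | First dose to 7 days after last dose | Day 1 to 7 days after last anti-AdV therapy, or Week 16 if none |
| Daily e-diary, reviewed at each visit (8.7.1, 11.6) | Yes | Yes |
| Visit schedule (6.2) | Weekly to Week 16 | Same, except BCV dosing and PK |

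The first two rows tend to raise capture in BCV. The third can remove events from either arm, because an unblinded investigator decides the attribution and diarrhea is a common manifestation of AdV disease (4.2.3.1). The fourth can shorten observation in BCV. For example, suppose the first undetectable sample is at day 22 (the top of the range of medians in 4.3.3.2), it is confirmed 7 days later, and the last dose falls at about that time. The window then closes near day 22 + 7 + 7 = 36. An SoC child with no anti-AdV therapy is counted to Week 16 (Day 113). Section 4.3.1 puts typical onset of BCV-related diarrhea at 4 to 6 weeks, that is days 28 to 42. The last two rows work to equalize capture.

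**Step 3. Illustrate the size.** The plan gives no rate, power or capture figure for this endpoint, so there is no stated figure to reproduce. All rates here are assumed. Observed rate = true rate × share captured. With a true rate of 40% in both arms:

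- BCV, 95% captured: 0.40 × 0.95 = 0.38.
- SoC, 85% captured: 0.40 × 0.85 = 0.34, a difference of 4 points.
- SoC, 75% captured: 0.40 × 0.75 = 0.30, a difference of 8 points.
- Capture of 95% in both arms: no difference.
- Capture swapped (75% BCV, 95% SoC): 0.30 − 0.38 = −8 points.

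Across true rates of 20% to 50%, with BCV capture held at 95%, SoC capture of 85%, 75% or 65% gives a false excess of 2–5, 4–10 or 6–15 points. The observed risk ratios are 0.95/0.85 = 1.12, 0.95/0.75 = 1.27 and 0.95/0.65 = 1.46.

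For scale, with 94 and 47 children and observed rates of 38% and 30%, the 95% half-width is 1.96 × √(0.38 × 0.62/94 + 0.30 × 0.70/47) = 0.164. The 8-point shift is about half of that.

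**Step 4. Anchor on a documented difference.** Section 4.2.3.1 gives treatment-emergent diarrhea of any grade in CMX001-202 as 57% on BCV twice weekly and 28% on placebo, a difference of 29 points. If those were true rates, capture of 95% and 75% would show 0.57 × 0.95 − 0.28 × 0.75 = 0.5415 − 0.21 = 33 points. Unequal capture of this order would distort a large effect without creating it.

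**The case against.** The strongest reply is that the protocol already gives both arms structured diarrhea recording. The diary is daily, it is reviewed weekly by the staff who record AEs, and SoC follows the same schedule. The BCV cards are optional. Methods are deferred to the SAP (Section 12), safety comparisons are mainly descriptive (12.6), and every capture rate above is assumed. Much of this stands: it narrows the asymmetry and makes its size unknown. It does not name a source for the endpoint, nor remove the Grade 2 decision point that exists only under BCV, the attribution rule or the unequal TEAE windows.

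A reader might go further and infer that the endpoint can only come from the AE tables. The documents do not support that, since no source is named and the 12.6.1 tables do not contain the endpoint.

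A reader might also take the diary as an arm-neutral replacement for AEs. It is not. Unblinded children, caregivers or staff fill it in, and the BCV alert card goes to the same families. It covers only the stool-count part of Table 7, not ostomy output, incontinence, hospitalization or life-threatening consequences. It also does not hold the pre-transplant count that serves as baseline, which the note in 7.2 accepts may be unknown. Finally, counts over that baseline from Day 1 would score children enrolled with Grade 2 or 3 AdV-attributed diarrhea (allowed by exclusion criterion 2) as immediate events.

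**Conclusion.** The concern holds in a limited form. The endpoint's source is unspecified and by default appears to be open-label, investigator-graded AEs. Ascertainment can differ by arm, with partial offset from the shared diary, and the protocol text names no analysis of the diary's stool data. Whether a separate SAP does so cannot be judged, because the document reviewed contains only protocol Section 12.

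A reader might infer that reported BCV diarrhea will be inflated by 4 or 8 points. The documents do not support this. Those figures depend on assumed capture rates, and although prompting alone probably works against BCV, the attribution rule and the TEAE windows can work the other way. The net direction is uncertain. The point is still worth acting on before the primary database lock, because it concerns the main BCV toxicity and the needed data are already being collected.

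**What to change.** In 5.3.3 and 12.6:

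- Keep the investigator-graded AE analysis and state that AEs are its source. Tabulate it over the on-study window of Day 1 to Week 16 that 12.6.1 already defines, not the arm-specific TEAE windows.
- Add a pre-specified supportive analysis, from the e-diary, of incidence of and time to diarrhea that is Grade 2 or higher by stool count: an increase of at least 4 stools per day over the recorded pre-transplant count. Use one algorithm in both arms, Day 1 to Week 16, regardless of treatment status or attributed cause.
- For children with Grade 2 or 3 diarrhea at Day 1, count only new onset or worsening by at least one grade. Table 7 does not define Grade 4 by stool count, so say how a child at Grade 3 on Day 1 is handled.
- State rules for unknown baseline counts and missing diary days.
- Report agreement between diary-based and AE-based grading by arm.
- Describe the diary as collected symmetrically in both arms, but unblinded and limited to stool counts.

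The cost is a numeric baseline stool count for each child, one derivation, a small set of tables and the handling rules. Unknown baselines and missing days will lose some information. No dosing, interruption or stopping rule changes, and Section 12 allows SAP amendments until the primary database lock.

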8.3.2.1. Treatment-emergent Grade 1 GI-related AEs

Dosing with BCV may continue, while closely monitoring the subject for worsening of the AE(s).

Symptomatic care may be provided as needed (e.g., anti-emetics, anti-diarrheals). Hydration status should be closely monitored, and liquid and electrolyte intake should be encouraged, if appropriate, to avoid dehydration and the downstream consequences of dehydration on renal function.

Additionally:

- Nutritional advice should be given to avoid foods and drinks that affect intestinal water transport (e.g., caffeine, alcohol, carminative spices, and concentrated sugar syrups) as well as lactose- and sucrose-containing drinks because intestinal inflammation may result in down-regulation of intestinal disaccharidases
- Consideration should be given to adjusting medications associated with GI effects (e.g., macrolide antibiotics, magnesium sulfate salts and mycophenolate mofetil [MMF])
- Other causes of new GI symptoms should be investigated promptly and treated as appropriate (e.g., infections)

For treatment-emergent Grade 1 GI AEs, aggressive treatment of GVHD should be initiated only if the diagnosis is confirmed at another organ site (e.g., skin or liver). GI biopsy results, if endoscopy and biopsy are performed, may not differentiate GVHD from BCV-related toxicity because GI biopsies from subjects with BCV GI toxicity may show findings (such as crypt apoptotic bodies) that are also observed in biopsies from subjects with GVHD. If the subject is experiencing GVHD symptoms in other organ systems (e.g., skin or liver), biopsy specimens from those sites may be more informative.

In the absence of extra-intestinal involvement, starting or increasing steroids and/or other immunosuppressants for the treatment of GVHD should be delayed if medically feasible for Grade 1 diarrhea.

If steroid treatment of GVHD cannot be delayed (and BCV is continued) in subjects with Grade 1 symptoms, the subject's response to GVHD therapy should be closely monitored.

- If diarrhea persists for > 14 days at Grade 1, the complete subject profile should be reviewed, other etiologies for diarrhea considered, and if deemed appropriate, interruption of BCV should be considered in order to determine whether diarrhea resolves.

If diarrhea worsens to Grade 2 or higher, please see Section 8.3.2.2 below.

8.3.2.2. Treatment-emergent Grade 2 or Higher AEs of Diarrhea in Subjects with ≤ Grade 1 Diarrhea at Baseline

For subjects with CTCAE Grade 1 diarrhea or no diarrhea at baseline, BCV must be interrupted for treatment-emergent CTCAE Grade 2 or higher diarrhea. This includes new-onset Grade 2 or higher diarrhea or progression from Grade 1 to Grade 2 or higher diarrhea, regardless of the cause of the diarrhea.

In general, changing multiple therapies at the same time (e.g., interrupting BCV and starting steroids for new-onset or worsening GI GVHD) is not recommended. In order to assess response to BCV treatment interruption, start of (or increase in) steroid therapy for new-onset or worsening GI GVHD should be delayed, when possible.

- If diarrhea does not improve following ≥ 7 days interruption (at least 6 calendar days off BCV), a trial of steroid therapy for new-onset or worsening GI GVHD (while BCV is still being held) may be considered if deemed clinically appropriate.

If diarrhea does not improve to \leq CTCAE Grade 1 during interruption, BCV must not be resumed.

If diarrhea improves to \leq CTCAE Grade 1 in intensity, subjects may resume dosing of BCV, but no sooner than 7 days (i.e., at least 6 full days off drug) following the last BCV dose administration.

- If resumed, BCV must be administered in a consolidated QW dose (total weekly dose administered once weekly, i.e., 4 mg/kg, up to a maximum of 200 mg, QW in the absence of concurrent cyclosporine, or 2.8 mg/kg, up to a maximum of 140 mg, QW for subjects taking concurrent cyclosporine) to potentially improve tolerability, as weekly dosing intervals allow more time for GI mucosal regeneration between doses.

Treatment with the consolidated QW BCV dose will be continued through Week 16 post-randomization or until confirmed undetectable AdV viremia in plasma, whichever occurs first.

Recurrence of CTCAE Grade 2 or higher diarrhea after restarting BCV requires permanent discontinuation of BCV.

8.3.2.3. Treatment-emergent Diarrhea AEs in Subjects with Grade 2 or 3 Diarrhea Attributed to AdV at Baseline

For subjects with CTCAE Grade 2 or 3 diarrhea at baseline that is attributed to AdV, BCV dosing must be interrupted if:

- the diarrhea has not improved to \leq CTCAE Grade 1 after 21 days of therapy, or

- the subject experiences on-treatment worsening of one CTCAE grade or more at any time following initiation of BCV (i.e., Grade 2 worsens to \geq Grade 3, or Grade 3 worsens to \geq Grade 4), regardless of the cause of the diarrhea

If the diarrhea does not improve during interruption, BCV must not be resumed.

If diarrhea improves to \leq Grade 1 in intensity during interruption, subjects may resume dosing, but no sooner than 7 days (i.e., at least 6 full days off drug) following the last BCV dose administration.

- If resumed, BCV must be administered in a consolidated QW dose (total weekly dose administered once weekly, i.e., 4 mg/kg, up to a maximum of 200 mg, QW in the absence of concurrent cyclosporine, or 2.8 mg/kg, up to a maximum of 140 mg, QW for subjects taking concurrent cyclosporine) to potentially improve tolerability, as weekly dosing intervals allow more time for GI mucosal regeneration between doses.

Recurrence of CTCAE Grade 2 or higher diarrhea after restarting BCV requires permanent discontinuation of BCV.

See [Table 8](#) and [Table 9](#) for tabular summaries of the interruption and discontinuation thresholds for managing BCV in the setting of treatment-emergent diarrhea and recommendations for the management/evaluation of treatment-emergent GI AEs during BCV therapy.

Table 8: BCV Interruption and Discontinuation Thresholds for Treatment-emergent Diarrhea

Action Taken with BCV	\leq Grade 1 Diarrhea at Baseline	AdV-related Grade 2 Diarrhea at Baseline	AdV-related Grade 3 Diarrhea at Baseline
Temporary interruption	
 Interrupt if diarrhea worsens to \geq Grade 2 Consider interruption for Grade 1 diarrhea if persists for > 14 days, and starting treatment for acute GVHD 	
 Interrupt if diarrhea not \leq Grade 1 within 21 days of first dose of BCV Interrupt if diarrhea worsens to \geq Grade 3 at any time 	
 Interrupt if diarrhea not \leq Grade 1 within 21 days of first dose of BCV Interrupt if diarrhea worsens to \geq Grade 4 at any time
Resumption	
 May resume if diarrhea improves to \leq Grade 1, and after a minimum 7-day interruption (i.e., at least 6 full days off BCV) Must resume at 4 mg/kg (max 200 mg) QW or 2.8 mg/kg (max 140 mg) QW with concurrent cyclosporine administration 		
Permanent discontinuation	
 Permanently discontinue BCV if, following resumption of dosing, diarrhea \geq Grade 2 returns 		

Grade 1: Increase of < 4 stools per day over baseline; or mild increase in ostomy output compared to baseline

Grade 2: Increase of 4 to 6 stools per day over baseline; or moderate increase in ostomy output compared to baseline

Grade 3: Increase of \geq 7 stools per day over baseline; incontinence; hospitalization indicated; or severe increase in ostomy output compared to baseline; limiting self-care activities of daily living (ADLs)

Grade 4: Life-threatening consequences; urgent intervention indicated

Note: Action taken with BCV is regardless of the etiology of diarrhea.

Note: Pre-transplant stool output (= baseline).

Table 9: Recommended Management/Evaluation of Treatment-emergent GI Adverse Events during BCV Therapy

	Grade 1 Events	Grade 2 or Higher Events
Action with BCV	See Table 8 and Section 8.3.2	
Other interventions	
 • Avoid food/drinks that affect water transport (e.g., caffeine, alcohol, carminative spices, concentrated sugar syrups) • Avoid lactose- and sucrose-containing products • Adjust other medications associated with GI effects (e.g., macrolides, magnesium, MMF) • Symptomatic treatment dosed as needed (e.g., anti-emetics, anti-diarrheals) • Avoid starting steroid/immunosuppressants for GVHD (while dosing BCV) unless Grade 1 diarrhea persists for > 14 days 	
 • Same as for Grade 1 events • Interrupt other medications that may cause GI events (e.g., magnesium supplements, MMF) • Measure levels of immunosuppressants • Consider symptomatic treatment (e.g., anti-emetics, anti-diarrheals) dosed at regular intervals, if clinically appropriate • Fluid supplementation to maintain hydration
Other diagnostic evaluations	
 • Monitor hydration status, and supplement as needed • Evaluate for other infection • Evaluate for acute GVHD in other organ systems; consider non-GI biopsy 	
 • Same as for Grade 1 events

NOTE: When considering new-onset or worsening GI GVHD as the cause of GI symptoms:

- **Co-administration of BCV and steroids for GI GVHD is not recommended**
- In order to assess response to BCV treatment interruption, start of (or increase in) **steroid therapy for GI GVHD should be delayed, when possible**

If diarrhea does not improve following ≥ 7 days interruption (i.e., at least 6 full days off BCV), a trial of steroid therapy for new or worsening GI GVHD (while BCV is still being held) may be considered, if deemed clinically appropriate.

